## APPENDIX A: STUDY DEFINITIONS

Endpoints identified in the CEC Charter will be adjudicated by the independent CEC. A detailed CEC Charter will further define the endpoint definitions. In case of inconsistency between the protocol and the CEC Charter, the CEC Charter will be the final determining document.

### Access Site

#### *(Sponsor Definition)*

Site of insertion of study device components.

### Access Site and Vascular Complications

#### *(MVARC Definition)*

#### I. Vascular complications

##### x. Major access site vascular complications, including:

- i. Aortic dissection or aortic rupture, or
- ii. Access site-related† arterial or venous injury (dissection, stenosis, ischemia, arterial, or venous thrombosis including pulmonary emboli, perforation, rupture, arteriovenous fistula, pseudoaneurysm, hematoma, retroperitoneal hematoma, atrial septal defect‡), irreversible nerve injury, or compartment syndrome resulting in death; hemodynamic compromise; life-threatening, extensive, or major bleeding (MVARC bleeding scale); visceral ischemia; or neurological impairment, or
- iii. Distal embolization (noncerebral) from a vascular source requiring surgery or resulting in amputation or irreversible end-organ damage, or
- iv. Unplanned endovascular or surgical interventions resulting in death; life-threatening, extensive, or major bleeding (MVARC bleeding scale); visceral ischemia; or neurological impairment

##### xi. Minor access site vascular complications, including:

- i. Access site arterial or venous injury (dissection, stenosis, arterial, or venous thrombosis including pulmonary emboli, ischemia, perforation, rupture, arteriovenous fistula, pseudoaneurysm, hematoma, retroperitoneal hematoma, atrial septal defect‡) not resulting in death; life-threatening, extensive, or major bleeding (MVARC scale); visceral ischemia; or neurological impairment, or
- ii. Distal embolization treated with embolectomy and/or thrombectomy not resulting in amputation or irreversible end-organ damage, or
- iii. Any unplanned endovascular stenting or unplanned surgical intervention not meeting the criteria for a major vascular complication, or
- iv. Vascular repair (via surgery, ultrasound-guided compression, transcatheter embolization, or stent-graft)

## II. Cardiac structural complications due to access-related issues

### i. Major cardiac structural complications, including:

- i. Cardiac perforation\* or pseudoaneurysm resulting in death, life-threatening bleeding, hemodynamic compromise, or tamponade, or requiring unplanned surgical or percutaneous intervention

### ii. Minor cardiac structural complications, including:

- i. Cardiac perforation\* or pseudoaneurysm not meeting major criteria

*\*Including the left ventricle, left atrium, coronary sinus, right atrium, and right ventricle*

*†May arise from the access procedure per se or complications from vascular closure devices*

*‡Meeting pre-specified criteria for a hemodynamically significant shunt, or requiring unplanned percutaneous or surgical closure*

## Access Site and Vascular Complications Requiring Intervention

### (Sponsor Definition)

Complications (i.e. dissection, perforation, arteriovenous fistula, pseudoaneurysm formation, retroperitoneal hemorrhage, thromboembolism) requiring intervention (percutaneous or surgical).

*\*refer to MVARC definition above for definition of access site and vascular complications*

## Activity Monitoring

The continuous tracking of physical activity through the use of a patient deployed wearable monitoring device

## Acute Kidney Injury (AKI)

### (MVARC)

Defined per MVARC as maximal change in serum Creatinine (sCr) from baseline to 7 days post-procedure.

**Stage 1:** Increase in sCr to 150%–199% (1.50–1.99 x increase vs. baseline), increase of  $\geq 0.3$  mg/dl ( $\geq 26.4$  mmol/l) within 48 h, or urine output  $< 0.5$  ml/kg/h for  $\geq 6$  h but  $< 12$  h

**Stage 2:** Increase in sCr to 200%–299% (2.00–2.99 x increase vs. baseline) or urine output  $< 0.5$  ml/kg/h for  $\geq 12$  h but  $< 24$  h

**Stage 3:** Increase in sCr to  $\geq 300\%$  ( $> 3.0$  x increase vs. baseline), sCr of  $\geq 4.0$  mg/dl ( $\geq 354$  mmol/l) with an acute increase of  $\geq 0.5$  mg/dl (44 mmol/l), urine output  $< 0.3$  ml/kg/h for  $\geq 24$  h, or anuria for  $\geq 12$  h; patients receiving renal replacement therapy are considered stage 3 irrespective of other criteria

**Adverse Device Effect****(ISO 14155:2011)**

Adverse event related to the use of an investigational medical device.

NOTE 1- This includes any adverse event resulting from insufficiencies or inadequacies in the instructions for use, the deployment, the implantation, the installation, the operation, or any malfunction of the investigational medical device.

NOTE 2- This includes any event that is a result of a use error or intentional abnormal use of the investigational medical device

**Bleeding****(MVARC Definition)****I. Minor**

Any overt†, actionable sign of hemorrhage (e.g., more bleeding than would be expected for a clinical circumstance, including bleeding found by imaging alone) that meets  $\geq 1$  of the following: requiring nonsurgical medical intervention by a health care professional; leading to hospitalization or increased level of care; prompting evaluation; or requires 1 or 2 units of whole blood or packed red blood cell (RBC) transfusion and otherwise does not meet criteria for major, extensive, or life threatening.

**II. Major bleeding**

Overt bleeding either associated with a drop in the hemoglobin level of  $\geq 3.0$  g/dl or requiring transfusion of  $\geq 3$  units of whole blood or packed RBC AND does not meet the criteria of life-threatening or extensive bleeding.

**III. Extensive**

Overt source of bleeding with drop in hemoglobin of  $\geq 4$  g/dl or whole blood or packed RBC transfusion

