
Procedural Success
 
Device success with evidence of a reduction in TR grade by at least one grade (scale: none/trace, mild, moderate, severe, massive, torrential) at end of procedure, and without the need for a surgical or percutaneous intervention prior to hospital discharge. Per patient analysis.

Prosthesis
 
An artificial substitute

Re-intervention (Sponsor Definition)
 
Any intervention on the previously implanted study device (repair, alteration or replacement)

---

Renal Complication (Long-Term)
 
Long-term Renal Complication is defined as onset of renal replacement therapy (i.e hemodialysis, renal transplant)

New need for renal replacement therapy (Sponsor Definition)
 
New need for renal replacement therapy (i.e hemodialysis, renal transplant)

Screen Failure
 
A patient who has signed the consent but, does not fulfill enrollment criteria: does not meet the inclusion criteria or who meets at least one of the exclusion criteria.

Septicemia (Sponsor Definition)
 
Systemic infection requiring hospitalization and treatment with antibiotics.

Serious Adverse Event (SAE) (FDA 21 CFR 812.3)
 
An adverse event that
 
 
• Results in death
 
• Is life-threatening
 
• Requires inpatient hospitalization or prolongation of existing hospitalization
 
• Results in persistent or significant disability/incapacity 
 
○ Is an important medical event which may jeopardize the patient, and may require medical or surgical intervention to prevent one of the above outcomes
 
 
 

Severe Bleeding (Sponsor Definition)
 
Severe bleeding is a fatal, life-threatening, extensive, or major bleeding, as defined by MVARC.

SF-36
 
A survey with 36 questions that results in two scales of mental and physical functioning and overall health related quality of life.
 
SF-12: A 12 question abridged and validated version of the SF-36

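### The Extensive bleeding grade prints no transfusion unit count, so the 1–2 unit overt bleeds that Minor is written to hold become severe bleeding and 30-day MAEs

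*Protocol*

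**What the plan says.** The bleeding scale is in protocol Appendix A under Bleeding (MVARC Definition). Three adjacent grades use transfusion:

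- Minor (I) includes a bleed that "requires 1 or 2 units of whole blood or packed red blood cell (RBC) transfusion", provided that it "otherwise does not meet criteria for major, extensive, or life threatening".
- Major (II) needs a hemoglobin drop of at least 3.0 g/dl or a bleed "requiring transfusion of $\geq 3$ units of whole blood or packed RBC AND does not meet the criteria of life-threatening or extensive bleeding".
- Extensive (III) is "Overt source of bleeding with drop in hemoglobin of $\geq 4$ g/dl or whole blood or packed RBC transfusion".

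The link to the endpoints is explicit. Appendix A states: "Severe bleeding is a fatal, life-threatening, extensive, or major bleeding, as defined by MVARC". Severe bleeding is a component of the 30-day MAE composite (protocol Section 5.1, the MAE entry in Appendix A, and SAP Section 3.1). Clinical success requires procedural success and no MAE at 30 days (protocol Section 5.2.3, SAP Section 3.2.3).

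Two further provisions bear on the point. Protocol Section 12.4.1 and SAP Section 8.1 base the MAE analysis on CEC-adjudicated events. The opening paragraph of Appendix A says that the CEC Charter will elaborate the endpoint definitions and that it prevails where it and the protocol differ.

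**The concern.** Minor and Major each attach a unit count to transfusion; Extensive does not. The only number in the Extensive entry is a hemoglobin drop in g/dl, which cannot be carried over to units of blood. Because both lower grades yield to Extensive, an Extensive criterion met by any transfusion at all overrides their unit counts.

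Take a patient with an access-site hematoma, a 1.5 g/dl drop and one unit of red cells. The Minor entry is written to hold this patient, who would then not count towards the safety endpoint. As printed, the patient is Extensive, hence severe bleeding, hence an MAE and a clinical-success failure.

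This matters because the MAE composite is the study's only safety endpoint and is reported as a rate with a confidence interval and no hypothesis test. A grading rule that moves patients into the composite therefore goes directly into the reported safety result.

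**Working it through.** The documents give no expected MAE or bleeding rate, so there is no figure of the plan's own to reproduce. The check is to apply the rules as printed and then size one reclassified patient.

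**Step 1: the rules.** For an overt bleed with no life-threatening or fatal feature, let u be units transfused and h the hemoglobin drop in g/dl.

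- Extensive if h ≥ 4, or if u ≥ 1 (any transfusion, as printed).
- Otherwise Major if h ≥ 3 or u ≥ 3.
- Otherwise Minor, if one of the Minor conditions is met.

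**Step 2: compare** the grade with Extensive's transfusion limb set aside against the grade as printed.

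| Units | Drop (g/dl) | Limb set aside | As printed | Effect on MAE status |
|---|---|---|---|---|
| 0 | <3 | Minor | Minor | none |
| 0 | 3 to <4 | Major | Major | none |
| any | ≥4 | Extensive | Extensive | none |
| 1–2 | <3 | Minor | Extensive | non-event becomes MAE |
| 1–2 | 3 to <4 | Major | Extensive | label only |
| ≥3 | <4 | Major | Extensive | label only |

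As printed, no transfused overt bleed can be Minor or Major. Only the fourth row changes MAE status, because Major and Extensive are both severe bleeding.

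**Step 3: size per patient.** Protocol Section 12.1 allows up to 65 patients. One reclassified patient with no other MAE adds 1/65 = 1.5 percentage points to the MAE rate. If that patient had procedural success, clinical success falls by the same amount.

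**Step 4: illustration, on assumed counts.** SAP Section 6.1 specifies Clopper-Pearson intervals. For x of n patients, the limits are the 2.5% quantile of Beta(x, n−x+1) and the 97.5% quantile of Beta(x+1, n−x). With n = 65:

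| Other MAE patients (assumed) | Reclassified (assumed) | Rate | 95% CI |
|---|---|---|---|
| 0 | 1 | 1/65 = 1.5% | 0.0–8.3 |
| 0 | 5 | 5/65 = 7.7% | 2.5–17.0 |
| 4 | 0 | 4/65 = 6.2% | 1.7–15.0 |
| 4 | 1 | 5/65 = 7.7% | 2.5–17.0 |
| 4 | 2 | 6/65 = 9.2% | 3.5–19.0 |
| 4 | 3 | 7/65 = 10.8% | 4.4–20.9 |
| 4 | 5 | 9/65 = 13.8% | 6.5–24.7 |

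**Step 5: what a coherent scale needs.** Suppose Extensive required u ≥ T. At T = 2, a two-unit bleed still conflicts with Minor. At T = 3, Minor's 1–2 unit limb works but Major's transfusion limb stays empty. At any T of 4 or more, all three grades can be reached through transfusion. This tests consistency only; it does not identify the right figure.

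**Step 6: knock-on.** The major and minor categories of access site vascular complication in Appendix A use the same bleeding grades. A one-unit access-site hematoma could therefore also move from minor to major there. Within the composite a patient counts once, but the component counts could shift.

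**The case against.** Four points on the other side have weight.

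- **Text may have been lost.** The Extensive entry stops without a full stop, unlike the Minor, Major and Life-threatening entries, and it stops where a unit count would be expected. Loss in converting the PDF page to text cannot be excluded. The unit counts in the neighboring entries survived, and no redaction mark is visible, but neither fact settles it. This stands as a reason for medium confidence.
- **The definition is incorporated by reference.** Severe bleeding is tied to MVARC, and the consensus document is cited. A complete criterion may exist there. That would give the sponsor a source for the correction, but Appendix A is headed as the MVARC definition and is where the synopsis and Section 5 send the reader. The SAP adds nothing to it.
- **The CEC Charter controls.** It prevails over the protocol, and adjudicated data are analyzed. The charter may contain the full threshold. This limits what can be said about practice, though it does not make the three printed grades consistent with each other.
- **An adjudicator would see the omission.** The literal reading nullifies two explicit unit limbs, so a careful adjudicator may well not apply it. But that adjudicator would then need a figure that the protocol does not print.

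Three stronger readings are tempting. A reader might infer that the clash with Major also inflates the MAE rate. It does not, because Major is already severe bleeding. A reader might infer a large distortion, such as ten reclassified patients on top of four others (14/65 = 21.5%). No document gives a count of such bleeds, and that figure also needs every one of the ten to be free of other MAEs and the committee to apply the literal text. A reader might use the SAP's 15 patients to get 1/15 = 6.7 points each. That SAP was written for protocol version A, and the current version C allows up to 65.

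This is also a descriptive, single-arm feasibility study, and no performance goal is visible, so no formal test result depends on the definition.

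**Conclusion.** Wrong as written; it should be fixed, with medium confidence. The printed Extensive grade contradicts the 1–2 unit limb of Minor and empties the 3-or-more-unit limb of Major. Nothing else in the protocol or SAP supplies the missing criterion.

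The effect on the endpoints is confined to overt bleeds within 30 days with 1–2 units, a hemoglobin drop below 3 g/dl and no life-threatening or fatal feature. The step of 1.5 percentage points assumes the full 65 patients are evaluable and that the patient has no other MAE. The number of such patients is unknown. It is not shown that any event has been or would be misclassified, since that depends on a charter that is not among the documents.

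**What to change.** 1. Check the Extensive entry on the source page of Appendix A for words lost in extraction. If the unit count is there, the point closes.
2. If the gap is real, restore the complete transfusion criterion, with its unit count and any time period, from the cited MVARC document.
3. Read Minor, Major and Extensive together after the change and confirm that each can be reached through its transfusion limb. Check the access site vascular complication definitions against the result.
4. Confirm that the CEC Charter carries the same text.
5. Re-review any event that was graded Extensive on transfusion alone.

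The cost is one line in Appendix A, a matching check of the charter, and a second look at any transfused bleeds already adjudicated. No new data are needed.

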**IV. Life-threatening**

Bleeding in a critical organ, such as intracranial, intraspinal, intraocular, or pericardial necessitating surgery or intervention, or intramuscular with compartment syndrome OR bleeding causing hypovolemic shock or hypotension (systolic blood pressure  $< 90$  mm Hg lasting  $> 30$  min and not responding to volume resuscitation) or requiring significant doses of vasopressors or surgery.

**V. Fatal bleeding**

Bleeding adjudicated as being a proximate cause of death. Severe bleeding adjudicated as being a major contributing cause of a subsequent fatal complication, such as MI or cardiac arrest, is also considered fatal bleeding.

†“Overt” bleeding is defined as clinically obvious (visible bleeding and bleeding identified by imaging only).

Examples of overt bleeding include:

- Pseudoaneurysm
- Retroperitoneal hematoma seen on CAT scan
- Visible access site hematoma

Procedural bleeding has to be an overt bleeding from vascular system either at or remote from the access/surgical site. Thresholds for reporting procedural bleeding for study index procedure >100 ml total EBL (Estimated Blood Loss) from access site.

All post-procedural overt bleeding events must be reported including hematuria, melena, hematemesis, occult gastrointestinal bleeds or drop in Hgb with overt source of bleeding detected requiring transfusions etc. If the reason for Hgb drop was other than due to the overt bleeding i.e. due to hemodilution, chronic iron deficiency anemia etc., it will not be considered as a bleeding event.

### **Cardiac Tamponade**

#### ***(Sponsor Definition)***

Pressure on the heart that occurs when blood or fluid builds up in the space between the heart muscle (myocardium) and the outer covering sac of the heart (pericardium).

### **Causality Assessment**

Adverse events will be assessed by the Investigator for causality to the study device and index procedure as defined in MEDDEV 2.7/3 revision 3. The relationship between the use of the study device and study/implant procedure and the occurrence of each adverse event shall be assessed and categorized. During causality assessment, clinical judgement shall be used and the relevant study documents (i.e. Clinical Protocol, ICF, IFU and/or IB) shall be consulted for the listing of foreseeable adverse events/potential risks. The presence of confounding factors, such as concomitant medication/treatment, the natural history of the underlying disease, other concurrent illnesses or risk factors shall also be considered.

**Not related:** relationship to the device or procedures can be excluded when:

- the event is not a known side effect of the product category the device belongs to or of similar devices and procedures;
- the event has no temporal relationship with the use of the investigational device or the procedures;
- the serious event does not follow a known response pattern to the medical device (if the response pattern is previously known) and is biologically implausible;
- the discontinuation of medical device application or the reduction of the level of activation/exposure - when clinically feasible - and reintroduction of its use (or increase of the level of activation/exposure), do not impact on the serious event;
- the event involves a body-site or an organ not expected to be affected by the device or procedure;

- the serious event can be attributed to another cause (e.g. an underlying or concurrent illness/ clinical condition, an effect of another device, drug, treatment or other risk factors);
- the event does not depend on a false result given by the investigational device used for diagnosis, when applicable;
- harms to the patient are not clearly due to use error;

In order to establish the non-relatedness, not all the criteria listed above might be met at the same time, depending on the type of device/procedures and the serious event.

**Unlikely:** the relationship with the use of the device seems not relevant and/or the event can be reasonably explained by another cause, but additional information may be obtained.

**Possible:** the relationship with the use of the investigational device is weak but cannot be ruled out completely. Alternative causes are also possible (e.g. an underlying or concurrent illness/ clinical condition or/and an effect of another device, drug or treatment). Cases where relatedness cannot be assessed or no information has been obtained should also be classified as possible.

**Probable:** The relationship with the use of the investigational device seems relevant and/or the event cannot reasonably explained by another cause, but additional information may be obtained.

**Related:** the serious event is associated with the investigational device or with procedures beyond reasonable doubt when:

- the event is a known side effect of the product category the device belongs to or of similar devices and procedures;
- the event has a temporal relationship with investigational device use/application or procedures;
- the event involves a body-site or organ that
  - the investigational device or procedures are applied to;
  - the investigational device or procedures have an effect on;
- the serious event follows a known response pattern to the medical device (if the response pattern is previously known);
- the discontinuation of medical device application (or reduction of the level of activation/exposure) and reintroduction of its use (or increase of the level of activation/exposure), impact on the serious event (when clinically feasible);
- other possible causes (e.g. an underlying or concurrent illness/ clinical condition or/and an effect of another device, drug or treatment) have been adequately ruled out;
- harm to the patient is due to error in use;
- the event depends on a false result given by the investigational device used for diagnosis, when applicable;

In order to establish relatedness, not all criteria listed above must be met at the same time, depending on the type of device, procedure and the serious event.

An adverse event can be related both to the study procedure and the study device. Complications of procedures are considered not related if the said procedures would have been applied to the patients also in the absence of investigational device use/application.

In some particular cases the event may not be able to be not adequately assessed because information is insufficient or contradictory and/or the data cannot be verified or supplemented. The sponsor and the Investigators will make the maximum effort to define and categorize the event and avoid these situations.

### **Clinical Frailty Scale©**

A 9 point single question administered to measure frailty. Developed by the Canadian Study of Health and Aging (CSHA).

### **Clinical Success**

Procedural success without MAEs at 30 days. Per patient analysis.

### **Death**

#### ***(MVARC Definition)***

All events with an outcome of death will be classified to determine whether the death was related to cardiovascular (CV) or non-cardiovascular (non-CV) cause.

Although categorizing the initiating or proximate cause of cardiovascular death may be difficult, major complications contributing to death should be identified. A diagnosis of non-cardiovascular death requires the primary cause to be clearly related to another condition (e.g., trauma, cancer, or suicide). For this study purpose, all deaths that are not unequivocally related to a non-cardiovascular condition are considered cardiovascular death.

